A potential way of improving maternal and perinatal outcomes among women with OL would be to buffer the excess lactic acid with sodium bicarbonate, achieving intrauterine resuscitation whilst awaiting an emergency cesarean section. However, in this situation, there is inadequate time (or staff) to correct the acidaemia through careful titration of the bicarbonate infusion. A universal safe and effective dose would therefore facilitate its use. In our previous RCT, a single dose of 4.2g was insufficient to achieve changes in maternal or neonatal lactate levels. It is not known if a higher dose of bicarbonate would reverse the acidosis (pH and lactate) and achieve clinical benefits for the mother and baby.

Methods

An early phase III, placebo-controlled dose-ranging trial is proposed to determine the efficacy and safety of a pre-operative infusion of sodium bicarbonate in women with obstructed labour (OL). In a ratio of 1:1:1: 1 100 mls (8.4g), 150 mls (12.6g) and 200 mls (16.8g) of 8.4% sodium bicarbonate solution, or placebo (50 mls of NS 0.9%). The primary outcome will be mean change in acidosis (pH and lactate levels) from baseline. The secondary outcomes will be neonatal death, safety of sodium bicarbonate, pharmacokinetics of sodium bicarbonate in pregnant women, primary PPH, sepsis, and maternal death.

Conclusion

Our results will inform the design of an effectiveness phase III trial to determine the effect of this preoperative infusion on maternal and perinatal outcomes.

Introduction

Unlike normal labour, obstructed labour is characterized by higher levels of lactic acid in maternal blood and amniotic fluid [1, 2]. Repetitive, prolonged, strong uterine contractions in obstructed labour impair oxygen supply to the placental bed which promotes anaerobic respiration and accumulation of lactic acid as a byproduct [3]. The accumulated lactic acid depletes the maternal and fetal buffer systems, with resultant metabolic acidosis [1, 3]. Without timely intervention to relieve the obstruction, coupled with diminishing maternal and fetal compensatory mechanisms, the accumulated hydrogen ions easily cross the placental barrier to cause fetal acidosis. The acidosis causes failure of basic cellular functions resulting into cell death.

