Therefore, we propose to undertake a placebo-controlled, dose-ranging pilot trial to determine the efficacy and safety of a preoperative infusion of sodium bicarbonate on acidosis, compared with placebo among women with obstructed labour (OL). We believe this is important because very often, in this situation, there is inadequate time (or staff) to correct the acidaemia through careful titration of the bicarbonate infusion. A universal safe and effective dose would therefore facilitate its use in a low resource setting. Our results will inform the design of a full-scale effectiveness phase III trial to determine the effect of this preoperative infusion on maternal and perinatal outcomes.

We hypothesize that a higher dose of bicarbonate, can safely lower the pH and lactate levels (metabolic acidosis) by at least 20%. Therefore, we aim to determine the effect and safety of a preoperative infusion of sodium bicarbonate on pH and lactate levels (metabolic acidosis) among women with obstructed labour.

Problem statement

In Uganda, obstructed labour (OL) directly accounts for 8% of all maternal deaths and up to 14.2% of the perinatal mortality rate [7]. In a recent RCT at Mbale hospital, we found that 61% of 477 women with OL were acidotic (lactate >4.8 mmol/L), with a median capillary blood lactate level of 6.9 (3.4–13) mmol/L [7]. In the same RCT, 34% of the newborns had an Apgar score of less than seven (7), and 12% resulted in early

BUFHS-2024-164_Protocol_SoBicOL-II Study_V1.3_10 September 2025_Page 4 of 25

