neonatal deaths despite being resuscitated. A potential way of improving maternal and perinatal outcomes among women with OL would be to buffer the excess lactic acid with sodium bicarbonate, achieving intrauterine resuscitation whilst awaiting an emergency cesarean section. However, in this situation, there is inadequate time (or staff) to correct the acidosis through careful titration of the bicarbonate infusion. A universal safe and effective dose would therefore facilitate its use. In our previous RCT, a single dose of 4.2g was insufficient to achieve changes in maternal or neonatal lactate levels. It is not known if a higher dose of bicarbonate would reverse the acidosis and achieve clinical benefits for the mother and baby. Therefore, we propose to undertake a placebo-controlled, dose-ranging pilot trial to determine the efficacy and safety of a preoperative infusion of sodium bicarbonate on acidosis, compared with placebo among women with obstructed labour (OL).

Justification

Undertaking a placebo-controlled, dose-ranging pilot trial shall establish a universal safe and effective dose of sodium bicarbonate for use to correct the acidosis among women with obstructed labour. Our results will inform the design of a full-scale effectiveness phase III trial to determine the effect of this preoperative infusion on maternal and perinatal outcomes. Furthermore, this information will facilitate the inclusion of sodium bicarbonate infusion in the standard preoperative preparation for women with obstructed labour in a low resource setting.

Objectives

General objective

To determine the efficacy and safety of a preoperative infusion of sodium bicarbonate on pH and lactate levels (metabolic acidosis) among women with obstructed labour.

Specific objectives

1. To determine the efficacy of a preoperative infusion of sodium bicarbonate on acidosis, compared with placebo among women with obstructed labour (OL).
2. To determine the safety of a preoperative infusion of sodium bicarbonate compared with placebo among women with obstructed labour (OL).

Hypothesis

We hypothesize that a higher dose of bicarbonate can safely lower the lactate levels (metabolic acidosis) by at least 20%.

Methods and materials

Study design

We will conduct a dose-finding phase III, randomized, double-blind, placebo-controlled, parallel-group trial.

Study setting

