We will recruit 280 participants; 70 in each of the four arms. Wiberg-Itzel et al [2] observed mean umbilical artery pH 7.23 (SD 0.07) in the non-intervention group. With our sample size, we will have 80% power (significance level 0.05) to detect mean pH changes of 0.04 and above in each arm. We are interested in detecting an effect size of 0.2 and above, which we deem to be a moderate effect size. The total sample size needed to detect a between-factor mean effect size of 0.2, by repeated measures analysis of variance (ANOVA) with a type 1 error margin of 5%, across 4 groups with 5 repeated measurements; was 224 at a power of 91%. Assuming a 20% loss to follow up in our study; we will need 280 participants (70 in each of the 4 groups). The sample size was calculated using G* Power software version 3.1 using the test family for the F test, and the statistical test for ANOVA repeated measures, between factor analysis & within-between interaction [10]. Therefore, our sample size will also be sufficient to detect a within and between-subject interaction (intervention and time interaction) with a power of 99%. To obtain these estimates, we will construct an interaction term between the intervention and the time variable. We are confident that we shall be able to accrue this number of participants in a period of six calendar months, on the basis of our experience working in the same hospital [7]. In order to detect a change in maternal pH, a minimum of two measurements are needed from a participant. However, with improvement of obstetric care, many women deliver within 30 minutes of taking the baseline measurements and hence no second measurement is obtained. To account for this form of right censoring, we have inflated our sample size by 192 participants to ensure that we have at least 280 women with at least two pH measurements. We will recruit 472 participants; 118 in each of the four arms.

Outcome variables

The primary outcome measure will be the mean change in maternal pH from baseline in each group. The secondary outcomes will include, mean pH and lactate in maternal and umbilical blood, early neonatal death, safety (side effects) of sodium bicarbonate, primary PPH, sepsis and death. Furthermore, the plasma concentrations of HCO₃ levels will be measured as well to accurately estimate the required dose.

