Data analysis plan

Data will be analyzed using Stata version 17.0 (StataCorp; College Station, TX, USA). We will describe categorical variables as proportions and compare them with chi-squared tests or Fischer's exact tests as appropriate. We will describe continuous variables as means (SD) OR medians (IQR) and compare them with t tests or Mann-Whitney U tests as appropriate. Our analysis will be by intention to treat. To determine the safety of sodium bicarbonate infusion, we will compare the incidence of side effects in each arm and report risk differences.

For the primary outcome of acidosis (pH and lactate) between-subjects repeated measures ANOVA will be conducted. We will also conduct within-subject interaction repeated measures ANOVA to assess for differences in the rate of change of pH between the groups.

We will use histograms, P-P plots, k-density, and Q-Q to assess the distribution of normality of continuous outcomes. In case the distribution of normality is not met; we shall transform our data and this decision will be guided by Stata's *gladder* command that shows various transformation options.

All analyses will be followed by a Bonferroni posthoc test for multiple comparisons, a Friedman test to compare rates of change between the various groups, and a Mauchly's test of Sphericity to check for equal variance among the combinations of the various groups. We will use Margins and Margins plots to obtain marginal means and graphical descriptions of the interaction between various groups and time.

Data Monitoring

Independent Data Monitoring Committee (IDMC)

An independent data monitoring committee (IDMC) will be appointed consisting of 3 members: a statistician, an obstetrician/gynaecologist, and a paediatrician. They will operate according to the IDMC charter, which will be developed with the members. IDMC will be encouraged to follow the recommendations of the international DAMOCLES group for IDMC activities.[12] The IDMC will monitor the trial once with a focus on issues relating to the quality of trial conduct, such as overall and site-specific rates of recruitment, adherence to trial interventions, visit schedules, losses to follow-up, and administrative and safety data. It will review administrative and safety data approximately every three months. The treatment groups will be masked in the IDMC reports.

Interim analyses and stopping guidelines

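### The primary outcome is maternal pH in one section and pH with lactate in two others, and no rule says how the two endpoints relate

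*Combined protocol and SAP*

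**What the plan says.** The current text describes the primary outcome in several ways.

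- **Outcome variables:** "The primary outcome measure will be the mean change in maternal pH from baseline in each group". The next sentence puts lactate among the secondary outcomes: "The secondary outcomes will include, mean pH and lactate in maternal and umbilical blood, early neonatal death".
- **Abstract, Methods:** "The primary outcome will be mean change in acidosis (pH and lactate levels) from baseline".
- **Data analysis plan:** "For the primary outcome of acidosis (pH and lactate) between-subjects repeated measures ANOVA will be conducted".
- **Hypothesis:** a higher dose "can safely lower the lactate levels (metabolic acidosis) by at least 20" per cent. Maternal pH is not mentioned.
- **Introduction, hypothesis sentence:** a higher dose "can safely lower the pH and lactate levels (metabolic acidosis) by at least 20" per cent.

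The Data analysis plan adds a Bonferroni post hoc step, set among the comparisons between groups. Interim analyses and stopping guidelines allow the trial to stop on p ≤ 0.003 for the primary outcome between the arms, and do not say whether that is pH, lactate or both.

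**The concern.** The definition of the primary outcome decides which test governs the trial's conclusion and which one the monitoring committee's statistician applies at the interim look. Here that person would have to choose. The choice could matter, because the two endpoints may not move together: the Introduction reports that in the earlier trial the lactate effect was visible only after more than an hour, while the sample size section says many women deliver within 30 minutes of baseline.

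If both endpoints are treated as primary and either is enough, the chance of a false positive claim exceeds 5%. Nothing in the plan rules that reading out. The Bonferroni step appears to cover arms, not endpoints.

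The Introduction's hypothesis adds confusion. A lower pH means worse acidosis, which is the opposite of what the trial sets out to achieve.

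**Working it through.** **1. The plan's own figure.** Inputs from Sample size estimation and sampling: effect size f = 0.2, alpha 0.05, k = 4 groups, m = 5 measurements, N = 224, stated power 91%. The documents give no correlation between repeated measurements, so rho = 0.5 is assumed. For the between-group repeated measures F test:

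- noncentrality = N·m·f² / (1 + (m − 1)·rho) = 224 × 5 × 0.04 / 3 = 14.93, with 3 and 220 degrees of freedom;
- power = 0.9106, which reproduces the stated 91%;
- 224 / (1 − 0.20) = 280, which reproduces the stated total after loss to follow-up.

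The plan's sizing is therefore correct for one endpoint tested at 0.05.

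**2. Error if either endpoint is enough.** With two independent tests, 1 − 0.95² = 0.0975. For correlated two-sided normal tests, the probability that at least one is significant is about 0.091 at correlation 0.5 and about 0.070 at 0.9. Treating each endpoint as a three-degree-of-freedom group test gives nearly the same: 0.091 and 0.071. The correlations are assumptions.

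**3. Error under the other readings.** If pH alone is primary, as under Outcome variables, there is one test and the error is 0.05. If both endpoints must be significant, the error for the joint claim does not exceed 0.05. The price is power: at N = 224, assuming f = 0.2 for both, joint power runs from 0.9106² = 0.829 (independent) to 0.911 (fully correlated).

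**4. Splitting alpha.** At 0.025 per endpoint, with the same formula and rho = 0.5, power is 85.6% at N = 224 and 93.4% at N = 280 evaluable. Getting back to 91% takes 260 evaluable women, or 260 / 0.80 = 325 with 20% loss. Both figures are before the plan's further inflation for early delivery.

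**5. The Introduction's 20% applied to pH.** The only pH mean in the plan is 7.23 (SD 0.07, umbilical artery). A 20% fall gives 7.23 × 0.80 = 5.78. The difference used in the sample size section is 0.04, and 0.04 / 7.23 is about 0.6%. The 20% cannot be meant for pH. Applied to the earlier trial's median lactate of 6.9 mmol/L it gives 6.9 × 0.80 = 5.52, a coherent target in the right direction.

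**6. What the 0.04 does and does not do.** With SD 0.07, a difference of 0.04 at 80% power needs 2 × (1.960 + 0.842)² × 0.07² / 0.04² = 48.1, so 49 per arm. Seventy per arm gives 92%. The 0.04 is thus not what produced 280, which comes from the unit-free f = 0.2.

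**The case against.** The best reply is that Outcome variables is the section meant to define endpoints. It names one, maternal pH, and makes lactate secondary. Read that way there is one primary test and nothing to correct for. The inflation for women with at least two pH measurements points the same way. This has force, and it is why the error figures are conditional. It does not settle the matter, because the section that specifies the primary analysis names both endpoints, and so does the abstract.

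A reader might also infer four stronger things, none of which the documents support.

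- *The trial has two primary tests and no error control.* Two tests follow only from the abstract and the Data analysis plan, and no section says that either one suffices. There is a Bonferroni step; the gap is specific to pH versus lactate.
- *The success direction is reversed.* This rests on one Introduction sentence. The abstract speaks of reversing the acidosis, the formal Hypothesis has lactate falling, the F tests have no direction, and the interim bounds are symmetric at −2.96 and 2.96. No decision rule is reversed.
- *The primary analysis is within arms, so it cannot be separated from the saline all women receive.* The wording of the outcome describes the measure, not the contrast. Objective 1 compares with placebo, and the sizing, the analysis plan and the stopping rule all concern differences between groups.
- *The sample size is for pH only.* The 224 and 280 rest on f = 0.2, which belongs to no particular endpoint. Only the 0.04 statement and the later inflation by 192 women are tied to pH.

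**Conclusion.** The primary outcome is inconsistent in the current text, and the relation between pH and lactate is unspecified. The gap carries into the stopping rule. This is an unresolved definition; it does not show that the trial will run two uncorrected tests.

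The size depends on how the definition is resolved. The familywise error is 7.0% to 9.75% if either endpoint at 0.05 suffices, over assumed correlations from 0.9 down to 0, and there is no inflation if pH alone is primary or both are required. The power figures assume rho = 0.5 and f = 0.2 for each endpoint.

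The Introduction's hypothesis is wrong for pH in both direction and size, but it is a wording error that changes no test.

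**What to change.** Before any unblinded look, use one definition in the abstract, Hypothesis, Outcome variables, Data analysis plan and stopping guidelines.

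**Simplest option.** The primary outcome is the between-group difference (bicarbonate arms versus placebo) in change of maternal pH from baseline, tested at 0.05 by the planned between-group repeated measures analysis. State which of the Table 1 times enter. Make maternal lactate the first secondary outcome, tested only if the primary pH test is significant, and say at what level it would be tested if the trial stops at the interim. This fits Outcome variables and the pH-based inflation, and it leaves 224 and 280 as they are.

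**If the sponsor wants both endpoints as primary.** Either state that both must succeed (joint power about 83% to 91% at 224), or split alpha (85.6% at 224; 260 evaluable, 325 with 20% loss, to keep 91%). Restate the power in either case.

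**Wording.** Rewrite the Introduction's hypothesis as a rise in pH and a fall in lactate, with the 20% applying to lactate only. Do not turn 0.04 into a success threshold: it is a detectable difference based on an umbilical artery SD. Keep the four-group test as the primary test, with the Bonferroni comparisons following it.

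**Cost.** The simplest option is a wording amendment with no added participants. The loss is that lactate can no longer support a stand-alone primary claim.

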Mbale regional referral and teaching hospital is a busy center in Eastern Uganda with a catchment population of over 4-5 million people. Based on the annual hospital medical records, over 10,000 births occur annually with a caesarean section rate of 35%; about 12% of these operations are due to obstructed labour.

Study population

Eligibility criteria:

Inclusion Criteria:

We will include patients with OL carrying singleton, term pregnancies (≥ 37 weeks of gestation) in cephalic presentation.

Exclusion Criteria:

We will exclude patients with other obstetric emergencies such as antepartum haemorrhage, preeclampsia and eclampsia (defined as elevated blood pressure of at least 140/90 mm Hg, urine protein of at least 2+, any of the danger signs and fits), premature rupture of membranes and intrauterine fetal death. Patients with comorbidities such as diabetes mellitus, sickle cell disease, renal disease, liver disease and heart disease. We will also exclude those patients with hypokalaemia (148 mmol/L) and alkalosis (bicarbonate >22 mmol/L) because they are more likely to develop adverse drug reactions.

Study procedures

A research team member will inform all patients and their attendants while in the waiting/admission area about the ongoing study as part of the routine health education talks in the unit. Mothers that express no further interest in participating in the study will be noted and not approached again about the same.

On the other hand, those that express interest in knowing more about the study will be approached by a study team member once a diagnosis of obstructed labour is confirmed by the attending physician. The mother will be given more information about the study and a verbal consent will be obtained using a pre-written script in their local language following the short verbal consent in **Appendix 2**. She will also be informed that the research midwife will approach her after the birth to seek formal consent to the use of the data and specimens collected during labour.

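### The pH outcome is a mean change with no upper bound and safety is compared on symptoms and signs only, so no planned result separates corrected acidosis from over-correction into alkalosis

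*Combined protocol and SAP*

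**What the plan says.** **Primary outcome.** Outcome variables: "The primary outcome measure will be the mean change in maternal pH from baseline in each group". No direction, range or limit is attached. The opening summary is wider: "The primary outcome will be mean change in acidosis (pH and lactate levels) from baseline". So is the Data analysis plan: "For the primary outcome of acidosis (pH and lactate) between-subjects repeated measures ANOVA will be conducted". The Introduction expects that a higher dose "can safely lower the pH and lactate levels (metabolic acidosis) by at least 20" per cent, while the Hypothesis section names lactate only.

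**Analysis.** The Data analysis plan lists repeated measures ANOVA, Bonferroni comparisons, a Friedman test, marginal means, and t or Mann-Whitney tests. Safety is the incidence of side effects by arm, reported as risk differences.

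**Safety items.** The lists under Adverse events/side effects and in Appendix 1, section I, contain symptoms and signs. Neither has a laboratory alkalosis item.

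**Entry.** "We will include patients with OL carrying singleton, term pregnancies", with no pH or lactate threshold. The one acid-base limit is an exclusion for "alkalosis (bicarbonate >22 mmol/L) because they are more likely to develop adverse drug reactions". On the previous trial, the plan reports that "61% of 477 women with OL were acidotic (lactate >4.8 mmol/L").

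**Readings.** Table 1 schedules blood gases and plasma bicarbonate at baseline, every 30 minutes to 150 minutes, and at birth.

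**Aim.** Under Justification, the trial "shall establish a universal safe and effective dose of sodium bicarbonate".

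**The concern.** Correcting an acidosis has an end point, but a mean change does not. Once a woman's pH is normal, a further rise still adds to the arm's mean. The plan treats high bicarbonate as a hazard at entry, gives fixed doses without titration, and admits women whose acidosis may be slight. Some over-correction is therefore a foreseeable result of the design.

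What is at stake is the dose conclusion. If two active arms differ in mean pH, the planned tables cannot show whether the larger change reflects more women corrected or more women carried past normal. The interim efficacy rule (p of 0.003 or less) also rests on the primary outcome, so the trial could stop for efficacy without that distinction having been examined.

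**Working it through.** The plan gives no figure for over-correction, so there is none to reproduce.

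**1. What the planned results can distinguish.** Take two invented women and an assumed upper reference pH of 7.45. One goes from 7.25 to 7.37, a change of +0.12. The other goes from 7.38 to 7.50, also +0.12. They add equally to the mean change, and the rank-based tests do not separate them either. If the second woman has no listed symptom, she does not appear in the safety comparison.

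**2. Could bicarbonate pass 22 mmol/L after dosing?** The doses come from the plan. With a molar mass of 84 g/mol, 8.4, 12.6 and 16.8 g are 100, 150 and 200 mmol. Everything else here is assumed. Initial rise = dose / (V × weight):

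- At V = 0.5 L/kg and 65 kg: 100/32.5 = 3.1, 150/32.5 = 4.6 and 200/32.5 = 6.2 mmol/L.
- Over 0.4–0.7 L/kg and 55–80 kg: 1.8–4.5, 2.7–6.8 and 3.6–9.1 mmol/L.

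Take baseline bicarbonate as normal with mean m and SD s, truncated at 22 by the exclusion. Then

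share above 22 = 1 − Φ((22 − rise − m)/s) / Φ((22 − m)/s).

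For m = 18, s = 2.5 and the top dose: 1 − Φ(−0.86)/Φ(1.60) = 1 − 0.194/0.945 = 79%.

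| Assumptions (65 kg) | 8.4 g | 12.6 g | 16.8 g |
|---|---|---|---|
| m 18, s 2.5, 0.5 L/kg | 32% | 57% | 79% |
| m 16, s 3, 0.5 L/kg | 15% | 31% | 51% |
| m 20, s 2, 0.5 L/kg | 65% | 89% | 98% |
| m 18, s 2.5, 0.5 L/kg, half the rise retained | 11% | 21% | 32% |
| m 18, s 2.5, 0.7 L/kg, half the rise retained | 7% | 13% | 19% |

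The top-dose share runs from 19% to 98% across these rows. It would be lower still if the lowest baseline were paired with half retention at 0.7 L/kg: rise 0.5 × 200/45.5 = 2.2, share 8%. That shares increase with dose is built into a model where the rise is proportional to dose, so it is not evidence.

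**3. The same question on pH.** The SD of 0.07 is the plan's umbilical artery figure, borrowed here for maternal pH. The range 7.35–7.45 and the undosed means are assumed. Share above = 1 − Φ((7.45 − mean − shift)/0.07).

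| Undosed mean | Result | Shift 0 | 0.04 | 0.08 | 0.12 |
|---|---|---|---|---|---|
| 7.32 | above 7.45 | 3% | 10% | 24% | 44% |
| 7.32 | in range | 30% | 46% | 52% | 46% |
| 7.36 | above 7.45 | 10% | 24% | 44% | 67% |
| 7.36 | in range | 46% | 52% | 46% | 30% |
| 7.40 | above 7.45 | 24% | 44% | 67% | 84% |
| 7.40 | in range | 52% | 46% | 30% | 15% |

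In each block the largest shift has the largest mean change but not the largest share in range. How far the two part depends on the starting pH.

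**4. Would the added outcome be informative?** For 10% against 24% above a limit (9.9% and 23.8% unrounded, two-sided 5%), power is 82% at 118 per arm and 60% at 70 per arm. At 70 per arm the 95% interval for the difference is about ±1.96 × √(0.099 × 0.901/70 + 0.238 × 0.762/70) = ±12 percentage points. Seventy is the relevant lower figure: the plan adds 192 to reach 472 because many women deliver before a second pH reading, and 192/472 = 41%.

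**The case against.** A reader might infer that the plan scores the dose with the biggest pH rise as best, so that the largest dose wins by construction. The documents do not support that:

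- No section ranks doses or names a winner by pH. ANOVA with Bonferroni comparisons tests differences. Safety is a specific objective in its own right.
- The outcome is worded as a change, not a rise, and the Introduction speaks of lowering pH. An upward direction is inferred from the aim of reversing acidosis.
- The opening summary and the Data analysis plan make lactate primary too. The argument about passing normal does not carry over to lactate, and the earlier 4.2 g dose did not change lactate significantly.
- Not every analysis compares means, since Friedman and Mann-Whitney tests are named.
- The 22 mmol/L limit is an entry criterion. The plan does not apply it after dosing.
- Bicarbonate has a stated use: estimating the required dose, through the pharmacokinetic analysis.

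All of this stands, and it limits the point to a missing outcome. It does not fill the gap. Neither the rank tests nor the lactate result identifies over-correction, the pharmacokinetic section sets no threshold, and the side-effect lists contain no biochemical item. The baseline exclusion keeps out women already above 22 mmol/L but says nothing about where the others end up.

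**Conclusion.** The point holds as a gap in the planned outcomes. The pH component of the primary outcome is unbounded, safety is compared on symptoms and signs, and nothing planned separates correction from over-correction, although the readings are scheduled. It does not show that the plan will choose the wrong dose, because the plan states no rule for choosing one.

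The size is unknown. The 19% to 98% range at the top dose rests on assumed baseline bicarbonate, body weight, distribution volume and retention, and on carrying the entry limit of 22 mmol/L over to post-dose values. The pH illustration rests on an assumed reference range and assumed undosed means. These figures show that over-correction is plausible enough to measure; they do not predict its frequency. The disagreement over whether pH alone or pH with lactate is primary, and the stated direction for pH, must be reconciled as well.

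**What to change.** Keep mean pH change, and state whether lactate is primary alongside it. Then pre-specify:

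- A biochemical over-correction safety outcome by arm: the proportion of women above an upper pH limit, and the proportion above an upper bicarbonate limit. The investigators set both limits before unblinding.
- One fixed reading time, for example 30 minutes, with later times as supportive. Counting any post-dose reading above a limit would not do: sampling continues until delivery, so women who wait longer have more chances to cross.
- Risk differences against placebo with 95% intervals, and the number of women without a post-dose reading in each arm.
- A statement that the conclusion about a safe and effective dose will weigh this outcome together with the pH and lactate results.

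The cost is one derived variable per limit and one table, with no extra sampling. Appendix 1, section F, has a pH column but none labelled bicarbonate, so the form should be checked. The downsides are one more secondary outcome, and no value for women who deliver before the first post-dose reading.
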